3.1.4 Schedule of Study Visits and Procedures

During the baseline and 6 months post-vaccination surveys, one visit will be performed. No follow-up will be done after this visit. During the two surveys, a questionnaire will be filled for each selected household to collect socio-demographics information on the household, including the number of members who live in the household, their age and sex, school or other day care attendance of the children living in the household, PCV vaccination status of children living in the household, exposure to solid fuel smoke, and smoking habits.

For each selected child aged 1 to 9 years, an additional questionnaire will be filled to collect information on the child’s recent symptoms of an upper respiratory tract infection, including receiving any antimicrobials in the previous two weeks, and a nasopharyngeal sampling will be performed.

Additionally at baseline, on a selected household member, a social interactions questionnaire will be filled to collect information on the number of contacts with people of different age groups in the last 24h.

During the post vaccination survey, additional information on the PCV vaccination during the study campaign from all children of the targeted age group will be collected.

Vaccination activities will occur at village level and will take place on a pre-scheduled day. All children of the target age group for vaccination, for instance aged 1-9 years of age, residing in the study villages allocated to full or fractional dose arm will be targeted for vaccination. Vaccination will occur at fixed sites in each participating village. Vaccination activities will be timed to happen in the same geographical area at the same

time and will be scheduled as to not interfere with other planned vaccination activities. The number of doses of vaccine administered at each site will be noted on tally sheets.

Data on Adverse Events (AEs) will be collected in a passive surveillance system for 7 days following vaccination (focusing on AEs at the injection site) and data on Serious Adverse Events (SAEs) for 28 days following vaccination. A health professional from the study team will be based in the nearest health centre to the vaccinated villages for 28 days after the vaccination activities and will be the key notifiers of AEs and SAEs to the study team. Moreover, the community health workers from the vaccinated villages will be asked to act as a focal point and communicate to the study team any events that occur during the follow-up period. During the vaccination activities, caretakers will be informed about vaccine safety and will be asked to contact the community health worker or to attend the nearest health centre in case of a health problem.

Data concerning SAEs from participants in villages allocated to the control group will be collected between the first vaccination date up to 28 days after the last vaccination date performed in villages that were allocated to full or fractional dose and located in the catchment area of the same health facility.

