7.13 Expected Results

The overall project will present results for each of the primary and secondary objectives. For the main trial, results of prevalence of vaccine-serotype pneumococcus will be presented and compared. The results of the qualitative study will be presented in the form of a report. All results will be communicated as described below in section 13.6.

8 Safety reporting for Adverse Events and Serious Adverse Event

Data on Adverse Events (AEs) will be collected in a passive surveillance system for 7 days following vaccination. Data on Serious Adverse Events (SAEs) will be collected in a passive surveillance system for 28 days following vaccination.

A health professional from the study team will be based in the nearest health centre to the vaccinated villages for 28 days after vaccination activities, and will be the key notifiers of AEs and SAEs to the study team. Moreover, the community health workers from the vaccinated villages will be asked to act as a focal point and communicate to the study team any events that occur during the follow-up period. During the vaccination activities, caretakers will be informed about vaccine safety and will be asked to contact the community health worker or to attend the nearest health centre in case of a health problem.

Following, the International Conference on Harmonization (ICH) Guidelines for Good Clinical Practice, an adverse event (AE) is defined as any untoward medical occurrence in a clinical trial subject to whom a vaccine has been administered; it does not necessarily have a causal relationship with the vaccine/vaccination.

Definitions of AEs and grading will be specified in an SOP. In this trial, the recording of AEs will be limited to the evaluation of injection-site reactions (pain, tenderness, induration, infection, etc).

A serious adverse event (SAE) is any untoward medical occurrence that:

- Results in death.
- Is life threatening: if the participant was at risk of death at the time of the event; it does not refer to an event that hypothetically might have caused death if it were more severe.
- Results in persistent or significant disability/incapacity: if the event results in a substantial disruption of the participant's ability to carry out normal life functions.

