3.2.2 Safety Assessments

The safety outcomes are AE(s) at the injection site occurring within 7 days after vaccination and SAE(s) occurring within 28 days after the vaccination. SAEs from participants in clusters allocated to the control group will be collected during a period of time from the first vaccination date up to 28 days after the last vaccination date performed in clusters allocated to full or fractional dose, in the geographical area sharing the same health center.

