4.3.3 Safety Analysis

Safety analysis will be based on the entire study population.

Any adverse events occurring within 7 days after vaccination, serious adverse events, or deaths will be summarized as n (%) of participants having experienced the AE(s), and SAEs or death by arms. Comparisons will be done between full-dose and fractional-dose arms with the control arm, using a Fisher's exact test.

All AEs will be coded to a "Preferred Term" (PT) and primary associated "System-Organ Class" (SOC) according to the MedDRA dictionary (Medical Dictionary for Regulatory Activities, version 25.0).

Counts and proportions will be provided overall and for each PT within each SOC. AE(s) will be tabulated overall and by grade, and by type of AEs:

- AEs non SAEs occurring with 7 days after vaccination
- SAEs
- SAEs leading to death

5. Statistical Tables to be Generated

<Consider appropriate tables for each of these categories and some examples are provided>

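### SAE detection and observation time both differ between vaccine and control arms, so the planned Fisher comparison with control is not like with like and its bias could run either way

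*Combined protocol and SAP*

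**What the plan says.** Protocol section 8 and SAP 3.1.4 set up passive SAE surveillance for 28 days after vaccination, with three reporting routes:

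- **Clinic.** SAP 3.1.4: "A health professional from the study team will be based in the nearest health centre to the vaccinated villages for 28 days". Protocol section 8 says the same and makes this person the key notifier.
- **Village.** SAP 3.1.4: "the community health workers from the vaccinated villages will be asked to act as a focal point and communicate to the study team any events".
- **Caretaker.** SAP 3.1.4: "During the vaccination activities, caretakers will be informed about vaccine safety and will be asked to contact the community health worker". Going to the nearest health centre is the alternative offered.

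For the control arm, SAP 3.1.4 adds: "Data concerning SAEs from participants in villages allocated to the control group will be collected between the first vaccination date up to 28 days after". Those 28 days run from the final vaccination in vaccinated villages served by the same facility. SAP 3.2.2 repeats this, tying the control window to vaccination "in clusters allocated to full or fractional dose, in the geographical area sharing the same health center". Protocol section 8 itself does not describe SAE collection in control villages. Protocol 7.11 and SAP 3.1.3 state that control villages get no dummy intervention.

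On analysis, SAP 4.3.3 states: "Comparisons will be done between full-dose and fractional-dose arms with the control arm, using a Fisher's exact test". Protocol section 12 plans the same test. SAP 3.1.5 takes vaccinated children as the denominator in the vaccine arms and census counts in the control arm. No section allows for unequal ascertainment.

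**The concern.** A comparison of SAE proportions between arms needs events to be found equally well, over equal time, in each arm. The plan departs from both conditions, in opposite directions.

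The village focal points and the caretaker briefing are described only where there is a campaign. A serious event that reaches a clinic may be picked up in either arm, provided the control village shares a facility with a vaccinated one. An event that never reaches a clinic, such as a death at home, has a named village reporter in vaccinated villages and none in control villages. This lowers the control count.

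The control window, by contrast, is never shorter than 28 days and is longer whenever vaccination dates in the catchment differ. This raises the control count.

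At stake are the SAE and death tables by arm. Their contrast with control would mix vaccine effect, reporting intensity and length of observation, and the documents give no means of separating them.

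**Working it through.** **Denominators.** Protocol 7.1 gives 27, 27 and 9 clusters and about 600 target-age children per cluster. The plan's own total is reproduced: 54 × 600 = 32,400. Per vaccine arm this is 27 × 600 = 16,200 (full coverage assumed). For control, 9 × 600 = 5,400 (census count read as target-age children).

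**Apparent risk ratio with no true effect.** Let s be control detection relative to vaccinated villages, and D the days from first to last vaccination in the catchment. With a constant background rate, the expected control proportion is s(28+D)/28 times that in a vaccine arm, so

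RR (vaccine/control) = 1 / [s(28+D)/28].

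Neither s nor D is in the documents; the values below are assumptions. Example: s=0.5, D=14 gives 0.5 × 42/28 = 0.75, and 1/0.75 = 1.33.

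| | D=0 | D=14 | D=28 |
|---|---|---|---|
| s=1 | 1.00 | 0.67 | 0.50 |
| s=0.75 | 1.33 | 0.89 | 0.67 |
| s=0.5 | 2.00 | 1.33 | 1.00 |
| s=0.25 | 4.00 | 2.67 | 2.00 |

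The two biases cancel when D = 28(1/s − 1): about 9 days for s=0.75, 28 days for s=0.5 and 84 days for s=0.25. A shorter spread leaves apparent harm; a longer one leaves apparent benefit.

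**What Fisher's test would do.** This was simulated at two-sided 0.05 (SAP 4.3 gives 0.05 but not the sidedness for safety), with 16,200 v 5,400 children, 4,000 trials per scenario, children treated as independent and no true effect. The 28-day SAE risk in vaccinated villages is not in the documents; 0.5 to 5 per 1,000 is assumed. Entries are the percentage of trials significant in the direction named.

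| s, D | Direction | 0.5/1,000 | 1/1,000 | 2/1,000 | 5/1,000 |
|---|---|---|---|---|---|
| 1, 0 | false harm | 0.7 | 1.1 | 1.8 | 2.3 |
| 0.5, 0 | false harm | 3.0 | 12.6 | 29.1 | 71.1 |
| 0.5, 14 | false harm | 2.1 | 4.5 | 7.0 | 18.5 |
| 0.5, 28 | false harm | 0.5 | 1.2 | 1.7 | 2.0 |
| 0.75, 28 | false benefit | 10.5 | 13.4 | 24.1 | 51.7 |
| 1, 14 | false benefit | 9.1 | 15.2 | 24.9 | 53.2 |
| 1, 28 | false benefit | 22.3 | 38.8 | 65.3 | 96.3 |

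The rows with s=1 and D above 0 bear on the fix: equalising detection while keeping the present control window would itself create a bias towards benefit.

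**Control clusters without a vaccinated neighbour.** The control window is defined only by vaccination in the same catchment. Randomisation is stratified by distance to a health centre and possibly by baseline prevalence, not by health area. Nothing therefore ensures that each control cluster has a vaccinated cluster in its catchment. One that has none has no defined window, and no study professional is specified for it. With 54 of 63 clusters vaccinated this may be uncommon; the documents do not say whether it occurs.

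**The case against.** The strongest reply is that the control arm is not left out. SAP 3.1.4 and 3.2.2 collect control SAEs through the shared facility, and protocol 9.5 places dedicated safety staff in health centres in the study area. Protocol 8.2.1 says all participants will be told to report serious signs, and 9.2 counts every resident of a randomised village as a participant. This stands against any claim that control SAEs go uncollected, which a reader might infer from the vaccinated-village wording. It does not remove the difference: the instruction in 8.2.1 is general, and no control-village reporter or briefing is named. The staff in 9.5 answer under-reporting overall, not unequal reporting by arm.

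A reader might also infer that the comparison would show false harm. The documents do not support a fixed direction. The longer control window works the other way. So may the restriction of the vaccine arms to children actually vaccinated, after screening for illness, while control counts all target-age children. Protocol 7.6 and SAP 3.1.4 plan simultaneous vaccination within an area, which suggests a short D and a small offset, but neither gives a figure.

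The consequences are also bounded. The safety objective is to assess occurrence after each dose, causality is judged case by case (protocol 8.1), and SAEs go to the DSMB as reports under its charter. Nothing says the DSMB relies on a control rate.

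**Conclusion.** The point holds as one of comparability. Detection and observation time both differ between the vaccine arms and control, the two differences pull in opposite directions, and the plan tests the contrast with no allowance for either.

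The size depends on assumed s and D. With detection halved, the apparent risk ratio under no effect runs from 2.00 (D=0) to 1.00 (D=28). With equal detection it runs from 1.00 (D=0) to 0.50 (D=28). The simulated error rates also assume the SAE risk, full coverage and independent children. They illustrate what the test could do and do not forecast a result.

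The full- versus fractional-dose contrast is not affected by this asymmetry, although SAP 4.3.3 does not list it, and the primary carriage analysis is untouched. This is a cheap improvement to a secondary safety comparison.

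**What to change.** In protocol section 8 and SAP 3.1.4, 3.2.2 and 4.3.3:

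1. **Match detection.** Ask the existing community health workers of the 9 control clusters to report SAEs and deaths in target-age children. Give caretakers there the same contact message at the village information sessions already planned in protocol 9.9.1.
2. **Match observation time.** Give each control cluster a 28-day window from an index date taken from vaccination in its catchment or, if there is none, in the nearest vaccinated health area. Steps 1 and 2 belong together, because step 1 alone leaves the longer control window.
3. **If either cannot be matched,** including where a control cluster has no study professional at its health centre, present the vaccine-versus-control SAE and death comparison descriptively, without Fisher's test, and state the unequal ascertainment.

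The cost is document wording plus a small extra request and follow-up in 9 clusters. The shorter control window yields somewhat fewer control events, and step 3 gives up the formal test against control.

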3.1.5 Analysis Populations

All data from the surveys will be analysed in an intent to treat approach, ie including all data collected in the household of each selected child. Only data collected in the households of selected children with results of the nasopharyngeal swab will be analysed for the primary outcome.

Analyses of the primary outcome will be repeated on the per protocol population. The per protocol population will include children that provided a NP sample and completed the child questionnaire as well as the household questionnaire and for which no protocol violation was reported and who were in clusters who received the intervention allocated during randomization.

Safety analysis will be conducted in two different groups depending on study intervention:

- In clusters allocated to the control arm, all children aged in the target age group for vaccination campaigns will be considered. The denominator in this study arm will be the population of the clusters according to the census records used to establish the sampling frame for the cluster.
- In clusters allocated to receive full- or fractional-dose mass campaigns, only children who actually received a vaccination will be considered, and the denominator in these study arms will be the number of children vaccinated based on records from the vaccination sites.

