3.1.1 Study cohorts

Clusters will be randomized to full dose mass vaccination campaigns, fractional dose mass vaccination campaigns or the control arm in 3:3:1 allocation ratio. Clusters will be composed of a village or group of closely-neighbouring villages that share a school or market, and will be limited to a population of between 500 and 4000 persons. Stratified randomization will be used to account for proximity to the nearest health centre (<5 km vs ≥5 km). In the event of significant imbalance in carriage of VT pneumococci between clusters in the baseline survey, randomization may also be stratified by baseline prevalence upon the decision of the Trial Steering Committee. For this reason, randomization will happen after the results of the baseline survey are known.

Vaccination will target all children aged 1 to 9 years of age residing in the selected villages. (If baseline survey data unexpectedly shows very low prevalence of carriage at the extremes of this age range, the target age group may be adjusted upon recommendation of the trial steering committee.) We estimate that children eligible for the vaccination campaigns will represent 30% of the total population. With an estimated average of 2000 people per cluster, vaccination will target approximately 600 children 1-9 years of age in each cluster receiving vaccine. In total, in the 54 clusters receiving vaccine, the mass vaccination campaign with single full- or fractional-dose PCV is expected to target approximately 32,400 children 1-9 years of age.

Prior to the mass vaccination campaign, a cross-sectional survey will be implemented to estimate community-level carriage of VT pneumococci, as well as to collect data on household composition, social interactions and PCV vaccination coverage in the routine EPI. A total of 36 households in each cluster will be invited to participate in the cross-sectional survey. For the purposes of this study, a household is defined as a group of people living under the authority of a head of household, sleeping under the same roof, and sharing at least one meal per day, for at least two weeks, independent of any family ties. Selection of households will be based on probability sampling. The required number of households in each cluster will be randomly selected using simple random sampling based on an exhaustive list of heads of household in the cluster.

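### SAP 3.1.5 counts control-arm safety events in target-age children but states a denominator with no age limit; taken literally, control SAE and death risk is understated 3.3-fold, partly offset by a longer control window.

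*Combined protocol and SAP*

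**What the plan says.** SAP 3.1.5 defines the safety groups by arm.

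- **Control clusters, who is counted:** "all children aged in the target age group for vaccination campaigns will be considered".
- **Control clusters, denominator:** "The denominator in this study arm will be the population of the clusters according to the census records used to establish the sampling frame".
- **Vaccine clusters, who is counted:** "only children who actually received a vaccination will be considered".
- **Vaccine clusters, denominator:** "the denominator in these study arms will be the number of children vaccinated based on records from the vaccination sites".

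SAP 3.1.4 sets the SAE window. Vaccinated children are followed for 28 days after their dose. Control SAEs are "collected between the first vaccination date up to 28 days after the last vaccination date" among vaccine-arm villages in the same health-facility catchment. SAP 3.2.2 repeats this rule.

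SAP 4.3.3 opens with "Safety analysis will be based on the entire study population", as does the safety paragraph in protocol section 12. It then summarises AEs, SAEs and deaths as n (%) by arm and compares each vaccine arm with control by Fisher's exact test.

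**The concern.** Within one bullet, the control numerator is limited to children and the denominator is not. The SAP's usage elsewhere favours the literal reading. In 3.1.1 the population of a cluster means all persons (500 to 4000). In 4.3.1 the total census population and the census population aged 1 to 9 are listed as two separate items. Nothing else in the protocol or SAP settles which one 3.1.5 intends.

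If child events are divided by persons of all ages, the control risk is too low and the comparison with control leans towards an apparent excess of SAEs or deaths after vaccination.

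The window rule is a second mismatch, in the opposite direction. Control children are observed for longer than 28 days wherever a catchment is vaccinated over more than one day, yet the comparison uses simple proportions that ignore observation time.

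**Working it through.** **Inputs from the documents**

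- Average cluster size, SAP 3.1.1: "With an estimated average of 2000 people per cluster".
- Target-age share, SAP 3.1.1: "We estimate that children eligible for the vaccination campaigns will represent 30% of the total population".
- Clusters, SAP 3.1.3: 9 control and 27 in each vaccine arm.

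**Reproducing the plan's own figure**

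2000 × 0.30 = 600 children per cluster, and 600 × 54 vaccine clusters = 32,400. This matches the campaign target in SAP 3.1.1, so the inputs are being used as the plan uses them. The documents state no control safety denominator to check directly.

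**Control denominator**

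- Literal: 9 × 2000 = 18,000 persons.
- Target age only: 9 × 600 = 5,400 children.
- Ratio: 18,000 / 5,400 = 1 / 0.30 = 3.33.

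The ratio depends only on the age share, not on cluster size. For an assumed share of 25% to 40% it runs from 4.0 to 2.5.

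**Offset from the control window**

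Let S be the number of days from first to last vaccination in a catchment. The control window is 28 + S days against 28 days per vaccinated child. At a constant event rate the control risk is inflated by (28 + S)/28, so the net understatement is 3.33 × 28/(28 + S). The documents do not give S; the values below are assumptions.

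| S (days) | Control window (days) | Inflation of control risk | Net understatement, literal denominator |
|---|---|---|---|
| 0 | 28 | 1.00 | 3.3 |
| 7 | 35 | 1.25 | 2.7 |
| 14 | 42 | 1.50 | 2.2 |
| 28 | 56 | 2.00 | 1.7 |

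The third column is also the bias that remains, now overstating control risk, if only the denominator is corrected.

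**What this could do to the Fisher test (illustration only)**

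Assumptions: the same true SAE risk in both arms, and full coverage, so 27 × 600 = 16,200 vaccinated children in one vaccine arm. The documents give no SAE rate. Expected counts are rounded to whole events.

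| Assumed risk per 28 days | S (days) | Vaccine arm | Control, literal | Risk ratio | p |
|---|---|---|---|---|---|
| 0.5 per 1000 | 0 | 8/16,200 | 3/18,000 | 3.0 | 0.13 |
| 1 per 1000 | 0 | 16/16,200 | 5/18,000 | 3.6 | 0.009 |
| 2 per 1000 | 0 | 32/16,200 | 11/18,000 | 3.2 | 0.0004 |
| 1 per 1000 | 7 | 16/16,200 | 7/18,000 | 2.5 | 0.037 |
| 1 per 1000 | 14 | 16/16,200 | 8/18,000 | 2.2 | 0.067 |
| 1 per 1000 | 28 | 16/16,200 | 11/18,000 | 1.6 | 0.25 |

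With 5,400 as the control denominator and no difference in window, the first three rows all give p = 1.0.

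**The case against.** The strongest reply is that this is loose wording and not a chosen analysis. The sentence just before the denominator rule names target-age children, so the rule may only be naming the census as the data source for that group. The SAP also uses the expected number of children aged 1-9 as the denominator for vaccination coverage (4.3.2.1). A careful analyst might well use the right count. This stands as a reason to call the bias conditional. It does not remove the need for a correction: SAP 1.1 gives the avoidance of post hoc decisions as a purpose of the plan, and choosing a safety denominator once events are known would be one.

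The second reply is that the longer control window works against the denominator error, and that SAP 3.1.4 has vaccination timed together within an area. Both points are right. A short span keeps the offset small and the denominator factor near 3.3; a long span does the reverse. But two errors of opposite sign, one of unknown size, do not protect the comparison.

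Three stronger readings are tempting, and the documents do not support them.

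- **That the trial will show a false, statistically significant vaccine signal.** Significance depends on an assumed SAE risk, assumed full coverage and an assumed span. It disappears at 0.5 per 1000, and at 1 per 1000 with a span of 14 days or more.
- **That the vaccine arms must also move to census children.** Analysing vaccinated children for safety is a defensible choice. Replacing it changes the estimand and would require SAE capture in unvaccinated children, whereas the SAP defines vaccine-arm follow-up from the child's vaccination.
- **That the wording of 4.3.3 is a further source of bias.** It conflicts with the specific definition in 3.1.5 and needs tidying, but it adds no separate error.

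**Conclusion.** The concern holds as a conditional error in a stated rule. Applied as written, the control denominator in SAP 3.1.5 understates control SAE and death risk by a factor of 3.3, resting on the SAP's own 30% age share. Allowing for the longer control window, the net factor is about 2.7, 2.2 or 1.7 for assumed vaccination spans of 7, 14 or 28 days at a constant event rate. If the denominator is corrected and the window is not, control risk is instead overstated by 1.25, 1.5 or 2.0 for the same spans. Any p-value is illustrative.

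The reach is narrow: only the comparison of SAEs and deaths with control. Recorded AEs are injection-site reactions and have no control counterpart. The full-dose versus fractional-dose safety contrast and the carriage analyses are untouched. The correction is worth making because the comparison is prespecified and the remedy is cheap.

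**What to change.** 1. **SAP 3.1.5.** State the control denominator as the census number of children in the campaign's target age group living in the control clusters. SAP 4.3.1 already calls for the census count of children aged 1 to 9 by cluster. Keep vaccinated children as the vaccine-arm denominator.
2. **SAP 3.1.4, 3.2.2 and 4.3.3.** Equalise observation time in the SAE and death comparison with control, by one of two routes fixed in advance. Either compare rates per child-time, with a rate-based test in place of Fisher's test on proportions; or count control events over a 28-day window in each catchment, with its start date defined beforehand, and keep Fisher's test.
3. **SAP 4.3.3.** Replace the reference to the entire study population with the safety population defined in 3.1.5.

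The cost is a few sentences and minimal extra analysis, with no new data. The 28-day route loses a few control events; the child-time route keeps them all.

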4.3.1 Baseline Characteristics

Information on the total number of participants per intervention group for each of the following categories will be presented: screened households, screen failures (together with reasons for screen failure), consented participants for the baseline survey, the vaccination and the follow up survey, screen failures (with reasons for screen failure) for baseline and post vaccination surveys and reasons for NP not performed.

Information on the total population and population aged 1 to 9 years from the census, as well as breakdown by sex and distance to nearest health facility will be also summarized by cluster.

Number of vaccinees, by sex and age group will be summarized by intervention group. Participant demographics and data collected through questionnaire at baseline and during post vaccination survey (as describe in section 3.2.3) for each group will be given at individual levels using count and percentages for qualitative variables,

mean and standard deviation (SD) for quantitative variables, and at cluster level using means and standard deviation (or median and IQR if appropriate).

Baseline prevalence of carriage (VT and non VT serotypes) will be measured as the proportion of participants that are respectively colonized with any of the 10 serotypes covered by PCV10 and colonized with any other serotypes, excluding non-typable SP and those confirmed as not colonized by SP.

Proportions will be compared using chi square or Fisher's exact test, as appropriate and adjusting for the clustering effect.

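### The control-arm safety denominator is worded without the age restriction that applies to its events; taken literally it is about 3.3 times too large, an error that the longer control SAE window only partly offsets if local campaigns are short

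*Combined protocol and SAP*

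**What the plan says.** SAP 3.1.5 defines the safety sets by arm. In control clusters, "all children aged in the target age group for vaccination campaigns will be considered". The next sentence reads: "The denominator in this study arm will be the population of the clusters according to the census records used to establish the sampling frame". In the two vaccine arms only vaccinated children count, and "the denominator in these study arms will be the number of children vaccinated based on records from the vaccination sites".

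SAP 4.3.3 reports SAEs and deaths as number and percentage of participants by arm, and adds: "Comparisons will be done between full-dose and fractional-dose arms with the control arm, using a Fisher's exact test". The same section opens by resting the safety analysis on the whole study population, which is not how 3.1.5 defines it.

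SAP 3.1.4 and 3.2.2 follow each vaccinee for SAEs for 28 days. In control clusters, SAEs are collected from the first vaccination date in the same health-facility catchment until 28 days after the last one.

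**The concern.** The control events come from children aged 1-9, while the denominator sentence names the cluster population with no age limit. Elsewhere the SAP keeps these quantities apart. Section 3.1.1 uses cluster population for all residents (500 to 4000 persons), and 4.3.1 lists the two census counts separately: "Information on the total population and population aged 1 to 9 years from the census". The coverage formula in 4.3.2.1 names the 1-9 age group when it wants that denominator. A programmer following 3.1.5 word for word would divide children's events by all residents in the control arm and by children in the vaccine arms.

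At stake is the only planned comparison of SAEs and deaths between vaccination and no vaccination, which serves a stated secondary objective. Under the literal reading with equal windows, equal risks would be reported as an excess in both vaccine arms. A true halving of risk by vaccination would be reported as a ratio of 0.5 x 3.33 = 1.67, the wrong side of 1.

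**Working it through.** **Inputs from the documents.** SAP 3.1.1: "With an estimated average of 2000 people per cluster, vaccination will target approximately 600 children 1-9 years of age in each cluster receiving vaccine"; also "children eligible for the vaccination campaigns will represent 30% of the total population". SAP 3.1.3: 27 clusters in each vaccine arm, 9 in control. SAP 3.1.4 and 3.2.2: the SAE windows described above.

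**Assumptions (not in the documents).** The 28-day SAE risk, equal in all arms: 0.05%, 0.1% or 0.2%. The local campaign length L within a catchment: 0 to 84 days. A constant event rate over time. Coverage of 100%, with 80% as a check. Clustering is ignored, so the p-values isolate the effect of the denominator and are not the trial's operating characteristics.

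**Step 1. Reproduce the plan's figure.** 2000 x 0.30 = 600 children per cluster; 600 x 54 = 32,400, the number in SAP 3.1.1.

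**Step 2. Size of the mismatch.** Control children: 9 x 600 = 5,400. Control residents: 9 x 2000 = 18,000. Ratio: 18,000 / 5,400 = 1 / 0.30 = 3.33. The control percentage is too low by 1 - 0.30 = 70%. If the target-age share were 25% or 35%, the ratio would be 4.0 or 2.9 and the understatement 75% or 65%.

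**Step 3. Effect on the planned test, equal windows, full coverage.** Vaccinees in one arm: 27 x 600 = 16,200. Expected events are risk x 16,200 in the vaccine arm and risk x 5,400 in control, rounded.

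| Assumed risk | Vaccine arm | Control events | Ratio, p with 18,000 | Ratio, p with 5,400 |
|---|---|---|---|---|
| 0.05% | 8/16,200 | 3 | 3.0, p = 0.13 | 0.9, p = 1.0 |
| 0.1% | 16/16,200 | 5 | 3.6, p = 0.009 | 1.1, p = 1.0 |
| 0.2% | 32/16,200 | 11 | 3.2, p = 0.0004 | 1.0, p = 1.0 |

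The ratios scatter around 3.33 because events are whole numbers. At 80% coverage (12,960 vaccinees) the literal-denominator p-values are 0.18, 0.014 and 0.0006.

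**Step 4. Allow for the longer control window.** Control children are observed for 28 + L days and vaccinees for 28. The apparent vaccine/control ratio at equal true rates is:

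- literal denominator: 1 / [0.30 x (28 + L)/28]
- target-age denominator: 28 / (28 + L)

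| L (days, assumed) | Literal denominator | Target-age denominator |
|---|---|---|
| 0 | 3.3 | 1.0 |
| 14 | 2.2 | 0.67 |
| 28 | 1.7 | 0.50 |
| 56 | 1.1 | 0.33 |
| 84 | 0.8 | 0.25 |

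The two errors cancel at L = 28/0.30 - 28 = 65 days. For L = 14 and a risk of 0.2%, expected control events are 5,400 x 0.002 x 42/28 = 16, and 32/16,200 against 16/18,000 still gives p = 0.009.

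The last column shows that correcting the denominator alone leaves an error in the other direction: the control rate is inflated and the vaccine arms look safer than they are.

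**The case against.** The strongest reply is that the two control-arm sentences belong together. The first says who counts, and the second may only name the source for counting them. The denominator sentence does not say total population, a term that 4.3.1 uses when it means all residents, and the 1-9 count is available from the same census. On that reading there is no denominator error. This stands as a possible reading, so a reader who infers that the control percentages will be 70% too low and that both vaccines will appear harmful goes further than the documents allow. It does not remove the point: the SAP's own usage favours the literal reading, and a plan meant to prevent post hoc choices should not leave two denominators 3.3-fold apart.

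The longer control window is a real offset, so the 70% and 3.3-fold figures hold only for equal windows. SAP 3.1.4 times vaccination in one geographical area together, which suggests a short local campaign and a partial offset, but no length is given. An offset that arises by accident from a second mismatch is no defence of the first.

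It is also fair that significance rests on an assumed risk. Surveillance is passive, protocol 9.5 concedes possible underreporting, and with few events the false excess may not be significant. The percentages in the table would still differ about threefold under equal windows.

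Finally, each SAE has an individual causality assessment and goes to the DSMB (protocol 8.1 and 8.5), so safety conclusions do not rest on this test alone. That limits the severity.

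**Conclusion.** The concern holds in conditional form. SAP 3.1.5 does not state the age restriction for the control denominator. Taken literally, the denominator is 3.33 times too large on the plan's figures of 2000 people per cluster and a 30% target-age share. Given equal windows, control SAE and death percentages would be about 70% too low. With the planned windows the spurious ratio is smaller: 2.2 at an assumed 14 days of local campaign, 1.7 at 28, and none at about 65. A significant false harm signal is possible but not certain; it depends on the unstated SAE risk (p = 0.13 at 0.05%, 0.0004 at 0.2%, full coverage and equal windows).

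The reach is limited to SAEs and deaths against control. The carriage analysis does not use this denominator. AEs are injection-site reactions, and the SAP provides for control-arm collection of SAEs only. Full versus fractional dose is unaffected because both arms use vaccinated children. Severity: should-fix.

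**What to change.** 1. In SAP 3.1.5, state that the control denominator is the census number of children in the vaccination target age group (1-9 years, or the adjusted group if the steering committee changes it) living in the control clusters. Use that count in 4.3.3. SAP 3.1.1 describes the sampling frame as a list of household heads, so also name the census table that supplies the age-specific count.
2. In SAP 4.3.3, replace the reference to the whole study population with the safety sets of 3.1.5.
3. Put the arms on the same time basis, for example SAEs and deaths per child-time at risk, with a rate comparison in place of Fisher's test on percentages. Without this, the corrected denominator leaves the control rate inflated by (28 + L)/28.

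The cost is small: a few sentences of SAP text. SAP 4.3.1 already plans to tabulate the census population aged 1-9 by cluster, and the vaccination dates that define each control window have to be known anyway. No new data collection and no change to the carriage analysis are needed.
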